	
is missing, immediate follow up is undertaken and queries to the site are raised. Investigators or other site personnel should inform designated person of any follow up information on a previously reported SAE immediately but no later than the end of the next business day of when he/she becomes aware of it.
 
If an SAE report is updated, the designated study personnel will be informed.
 
The appointed Medical Monitor will provide his/her causality assessment and make an expectedness assessment once the report is judged to be complete. The reference document for definition of expectedness is the Reference Safety Information in the current version of IB.
 
If any additional documentation is required (e.g. hospital discharge letter, autopsy report, etc.), designated person will request this information from the study site.
 
In case the eCRF cannot be accessed, the SAE should be reported by manually completing the paper SAE Form, provided in the investigator site file (ISF). completed, signed and dated paper SAE Form should, within 24 hours, be scanned and e-mailed to:
 
PPD [REDACTED]
 <hr/> 
Telephone: PPD [REDACTED]
 
E-mail: PPD [REDACTED]
 
A copy _____ be e-mailed to Parexel at: [contact]".
 
To
 
On discovery, all SAE/AESIs should be immediately reported (latest within 24 hours of knowledge of the event) to Parexel Safety Services by:
 
Entering the AE in the appropriate section (AE page and/or SAE page) of the eCRF, indicating that the event is considered serious, and
	

Section # and Name	Description of Change	Brief Rationale

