8.4.1.3 Adverse events of special interest (AESI)

An AESI (serious or non-serious) is one of scientific and medical concern specific to the Sponsor's product or program, for which ongoing monitoring and rapid communication by the Investigator to the Sponsor can be appropriate. Such an event might warrant further investigation in order to characterize and understand it.

All AESI, serious and non-serious, **must be reported within 24 hours** of identification using the same reporting process as for SAE reporting.

The following conditions should be considered AEs of special interest and require expedited reporting:

- a. ALT or AST $\geq 8 \times$ ULN
- b. ALT or AST $\geq 5 \times$ ULN for 2 or more weeks
- c. ALT or AST $\geq 3 \times$ ULN **and** total bilirubin $\geq 2 \times$ ULN (or ALT or AST $\geq 3 \times$ ULN **and** INR > 1.5)
- d. ALT or AST $\geq 3 \times$ ULN accompanied by clinical symptoms believed to be related to hepatitis or hypersensitivity, such as new or worsening of fatigue, nausea, vomiting, right upper quadrant pain or tenderness, fever, or rash
- e. ALT or AST $\geq 5 \times$ ULN but $< 8 \times$ ULN and cannot be monitored at least weekly for ≥ 2 weeks

Hy's Law, defined as $\geq 3 \times$ ULN ALT or AST **with coexisting** $\geq 2 \times$ ULN total bilirubin with no alternative explanation for the biochemical abnormality other than IMP (for example elevated ALP indicating cholestasis, viral hepatitis, other medication) must always be reported without delay as an AESI, and, if applicable, also as an SAE.

All potential drug-induced liver injuries (PDILI) events require immediate action, testing, and monitoring. If tests are done locally for more rapid results, a concurrent sample should also be sent to the central laboratory whenever possible.

PDILI events require notification of the Medical Monitor within 24 hours (e.g., by laboratory alert), and the patient must be discussed with the Medical Monitor as soon as possible. Patients with PDILI must be assessed to determine if the study drug must be discontinued (please refer to General withdrawal criteria, Section 7.1).

To ensure patient safety and enhance reliability in determining the hepatotoxic potential of an investigational drug, a standardized process for identification, monitoring and evaluation of liver events has to be followed.

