8.4.5 Recording Adverse Events

Adverse events must be recorded in the AE Log of the eCRF. The Investigator must provide information on the AE, preferably with a diagnosis or at least with signs and symptoms; start and stop dates, start and stop time; intensity; causal relationship to IMP; action taken, and outcome. If the AE is serious, this must be indicated in the eCRF.

Adverse events, including out-of-range clinically significant clinical safety laboratory values, must be recorded individually, except when considered manifestations of the same medical condition or disease state; in such cases, they must be recorded under a single diagnosis.

If the severity/intensity of an AE increases a new AE Form must be completed in the eCRF.

Adverse events must be documented in clear, unambiguous medical language, without use of abbreviations or acronyms.

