8.4.6 Reporting of Serious Adverse Events

On discovery, all SAE/AESIs should be immediately reported (latest within 24 hours of knowledge of the event) to Parexel Safety Services by:

Entering the AE in the appropriate section (AE page and/or SAE page) of the eCRF, indicating that the event is considered serious, and providing all the details per the eCRF completion guidelines

and

Completing the SAE report form and e-mailing/faxing the documents to Parexel Safety Services as per details below:

France (Paris) Mailbox: [contact]

France (Paris) Fax numbers: [contact] or [contact]

In the event that the site is unable to complete the SAE form or eCRF entry to report the event within 24 hours of their knowledge of the event, the Investigators may report the SAE over the telephone via the SAE answering service, and then provide the completed SAE form via **(fax or email)**, or complete the eCRF entry of the event (within the next 24 hours). If questions arise regarding the reporting procedures or the specifics of the reporting of an event, sites may call (English) utilizing the following numbers:

Paris: [contact]

In case the eCRF cannot be accessed, the SAE should be reported by manually completing the paper SAE Form, provided in the investigator site file (ISF).

The SAE report is reviewed by a designated person at Parexel to ensure that the report is valid and correct. For fatal or life-threatening SAEs where important or relevant information is missing, immediate follow-up is undertaken and queries to the site are raised by Parexel. Investigators or other site personnel should inform designated person of any follow-up information on a previously reported SAE immediately but no later than the end of the next business day of when he/she becomes aware of it.

If an SAE report is updated, the designated study personnel will be informed.

If any additional documentation is required (e.g., hospital discharge letter, autopsy report, etc.), designated person will request this information from the study site.

The study site should notify the CRA via phone or e-mail about the submission of the SAE report. As soon as the site personnel have access to the eCRF, the SAE should be reported electronically as well.

The Sponsor or Designee will assume responsibility for reporting SAEs to competent authorities (CAs) and the independent ethics committees (IECs) in accordance with local regulations.

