10.1.9 Study and Site Closure

The Sponsor or Designee reserves the right to discontinue the study at any time but intends only to exercise this right for valid scientific or administrative reasons.

After such a decision, the Investigator must inform all participating patients and perform relevant assessments, preferably according to the scheme for the final assessments. All delivered and unused study products and other study materials must be returned and all CRFs completed as far as possible.

The Investigator may initiate study site closure at any time, provided there is reasonable cause and sufficient notice is given in advance of the intended termination.

The study may be placed on hold for evaluation of possible risk to patients, prior to decision as to whether to terminate the study if any of the following criteria are met:

- At least 3 patients experience a similar unexpected AE, which is assessed as severe and is probable/possible related to the IMP.
- The occurrence of an SAE, if considered probable/possible related to the IMP.

A study termination will be initiated pending the outcome of any SAE investigation; termination will be based on the circumstances surrounding the event and findings with unblinding of the Sponsor medical monitor, if necessary.

The study will be discontinued for any of the following reasons:

- If overall 5 (five) X842-treated patients develop the same type of AESI and the frequency is at least 2 × higher than in the comparator group.
- If 3 (three) X842-treated patients meet Hy's Law criteria ($\geq 3 \times$ ULN for ALT or AST with total bilirubin $\geq 2 \times$ ULN and no other explanation for these elevations).
- If one or more clinically significant, life-threatening, or significantly disabling/incapacitating events that are likely related to X842 and that, in the opinion of

the Investigator in consultation with the Sponsor, may constitute sufficient reason to stop the study.

- If the Sponsor judges it necessary for medical, safety, regulatory, or other reasons consistent with applicable laws, regulations, and GCP.

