4.11.3 Deaths, Serious Adverse Events, and Other Significant Adverse Events

The following summaries will be provided by treatment group and overall.

- A summary of the number and percentage of deaths (including SAEs with fatal outcome and deaths as PT),
- A summary of the number and percentage of patients reporting a serious TEAE, by SOC and PT,
- A summary of the number and percentage of patients with TEAEs leading to discontinuation of study treatment, by SOC and PT.

The following listings will be provided:

- A listing of all deaths that occurred during the study,
- A listing of all SAEs,
- A listing of all AEs leading to discontinuation of study treatment.

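### Section 8.4.6 tells sites to mark every reported SAE or AESI as serious, which conflicts with the protocol's own provision for non-serious AESIs and can put non-serious liver AESIs into the SAE tables.

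*Protocol*

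**What the plan says.** Section 8.4.6 opens with a scope that joins the two kinds of event: "On discovery, all SAE/AESIs should be immediately reported (latest within 24 hours of knowledge of the event) to Parexel Safety Services by" two actions. The first is "Entering the AE in the appropriate section (AE page and/or SAE page) of the eCRF, indicating that the event is considered serious, and" then to give the details called for in the eCRF completion guidelines. The second is to complete and send the SAE report form. The Amendment 1.0 change table introduces this wording, and it stands unchanged in the current section.

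Section 8.4.1.3 begins "An AESI (serious or non-serious) is one of scientific and medical concern specific to the" sponsor's product or programme. It requires all AESIs, serious or not, to be reported within 24 hours "of identification using the same reporting process as for SAE reporting". On Hy's Law it says such a case "must always be reported without delay as an AESI, and, if applicable, also as an SAE".

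Section 8.4.5, on recording adverse events generally, says: "If the AE is serious, this must be indicated in the eCRF". Section 8.4.1.2 defines an SAE by a list of criteria that includes medical importance, and asks that doubtful cases be reported as SAEs.

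The flag is used in several places. SAP 4.11.1 has overview rows for SAEs and treatment-emergent SAEs. SAP 4.11.3 plans "A summary of the number and percentage of patients reporting a serious TEAE, by SOC and PT" and a listing of all SAEs. Among the criteria on which the study may be put on hold, Section 10.1.9 lists "The occurrence of an SAE, if considered probable/possible related to the IMP".

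**The concern.** The 24-hour route for AESIs is a matter of speed. Seriousness is a classification that has its own definition. Section 8.4.6 merges the two: an event sent by the fast route is, on the words, also declared serious.

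Non-serious AESIs are foreseeable here. All five AESI conditions in 8.4.1.3 are liver conditions. Condition e, a transaminase of at least 5 but below 8 times the upper limit of normal, turns partly on whether weekly follow-up is feasible, which is not a seriousness criterion. Section 2.3.1 records liver-enzyme rises with the active metabolite, linaprazan.

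At stake are the SAE rates by dose, since the protocol's rationale bases Phase 3 dose selection partly on each dose's safety data. Conduct is also affected. A related SAE meets a hold criterion. Under 8.4.6.1, a related SAE that the medical monitor also judges unexpected is a potential SUSAR, for which the sponsor's medical monitor is unblinded.

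**Working it through.** The documents give no AESI or SAE rate, and the sample-size sections are redacted, so there is no figure of the plan's own to reproduce. The main check is a comparison of texts.

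**Step 1: follow one non-serious AESI through the protocol.**

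- 8.4.1.3: the event is an AESI, may be non-serious, and goes through the SAE process.
- 8.4.6: that process says to indicate in the eCRF that the event is considered serious. No condition is attached.
- 8.4.1.2: the event meets no listed criterion and is not in doubt, so it is not an SAE.
- 8.4.5: the seriousness entry is tied to the event being serious. It does not say *only if*, but it gives no ground for flagging a non-serious event.
- 8.4.1.3, Hy's Law: even for this marked pattern, SAE status is an additional question.

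The 8.4.6 result (serious) and the 8.4.1.2 result (not serious) cannot both stand.

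**Step 2: does a later check restore the right flag?**

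- 8.4.6 offers the AE page and/or the SAE page. That is a choice of page, not of flag.
- 8.4.6 has SAE reports reviewed for validity and correctness, but does not say seriousness is reassessed.
- Section 10.3.4 lets the CRA, data manager or medical monitor raise a data clarification, but only site staff can change entries, and 8.4.6 tells those staff to indicate serious.
- SAP 4.11.2 has the sponsor medically evaluate potential AESIs before lock to identify which events are AESIs. Seriousness is not mentioned.

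Any of these might catch a wrong flag. None is stated to do so.

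**Step 3: the weight of one wrongly flagged patient.** Inputs are 48 patients per arm and about 240 in total (synopsis).

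- Within an arm: 1/48 = 2.1 percentage points.
- Overall: 1/240 = 0.4 percentage points.

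This is the weight of any single patient, not an estimate of bias.

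**Step 4: the hold criterion, for scale only.** The four X842 arms hold 4 × 48 = 192 patients. Let p be the per-patient probability of a non-serious AESI that is wrongly flagged and judged probably or possibly related. The value of p is an assumption, and patients are taken as independent. The chance of at least one such event is 1 − (1 − p)^192.

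| Assumed p | Chance of at least one among 192 |
|---|---|
| 0.1% | 17.5% |
| 0.25% | 38.2% |
| 0.5% | 61.8% |
| 1% | 85.5% |
| 2% | 97.9% |

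With correct flagging this contribution is zero. The range shows that a single-event criterion is sensitive to even rare misclassification; it does not say how rare that would be.

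**The case against.** The strongest reply is that 8.4.6 is loosely drafted and sites would not read it alone. Its heading concerns serious events, it offers either page, and it defers to eCRF completion guidelines that are not among the documents and may settle the tick-box. Sections 8.4.1.2, 8.4.1.3 and 8.4.5 all point to a conditional flag. Liver events are also closely watched: potential drug-induced liver injury goes to the medical monitor within 24 hours.

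Much of this stands as a limit on size. A reader might infer that non-serious liver AESIs will enter as SAEs, inflate the tables, trigger false holds and produce an apparent dose trend. The documents do not support that:

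- Misflagging is a possible result of one clause, not a certain one.
- Several AESIs, particularly the more marked or symptomatic ones, may properly be SAEs as medically important or doubtful cases under 8.4.1.2. Those are not inflation.
- The hold is discretionary and needs a probable or possible causality rating. A potential SUSAR further needs a judgement that the event is unexpected.
- The discontinuation rules in 10.1.9 based on five patients with the same type of AESI and three Hy's Law patients do not depend on the seriousness flag.
- AESIs have their own table and listing in SAP 4.11.2, so a reader could see which SAEs are liver AESIs. A dose trend created by misflagging is conjecture.

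The reply does not remove the contradiction. The operative reporting section states an unconditional instruction, and no described check is said to reverse it.

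**Conclusion.** Section 8.4.6 is wrong as written, to a minor-to-moderate degree. It is a conflict between current sections, not a missing detail. Followed literally, it gives the wrong seriousness status to any AESI that neither meets nor is in doubt under 8.4.1.2.

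The size per event is known: 2.1 percentage points in an arm at the planned 48 patients, and, if the event is judged related, enough by itself to meet a criterion on which the study may be held. The number of such events is unknown.

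The conclusion assumes that the eCRF completion guidelines do not already make the flag conditional. If they do, the conflict is one of protocol wording only, and the data should be unaffected.

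**What to change.** Reconcile 8.4.6 with 8.4.1.2, 8.4.1.3 and 8.4.5. Keep the 24-hour route and the report form for all AESIs, but have the site indicate serious only when an 8.4.1.2 criterion is met or in doubt. Align the eCRF completion guidelines with this.

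State in SAP 4.11.1 and 4.11.3 that the SAE outputs count events meeting 8.4.1.2. Verify the seriousness flag of every AESI against that section before those tables are produced. The SAP amendment was written after unblinding, so a check added now may fall after unblinding too. If it does, document each decision and mask the reviewer to dose where possible.

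The cost is a sentence in the protocol or the completion guidelines, a sentence in the SAP, and a review limited to the recorded AESIs.

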1.1 Synopsis

Protocol Title: A randomized double-blind, double dummy, active comparator-controlled dose-finding study in patients with erosive esophagitis due to gastro-esophageal reflux disease (GERD) Los Angeles grade C or D, and patients with at least partial symptom response but endoscopically still unhealed after 8 weeks history of standard treatment healing course with proton-pump inhibitor (PPI), to investigate safety, tolerability, and healing rates after 4 weeks treatment of X842 or lansoprazole, and symptom pattern during subsequent 4 weeks treatment with lansoprazole

Sponsor Study No.: CX842A2201

Phase: Phase 2

Sponsor: Cinclus Pharma AG

[name]
[name], Switzerland

Study Rationale:

This is a Phase 2, double-blind study in patients with erosive esophagitis due to GERD Los Angeles (LA) grades C or D, and in patients with at least partial symptom response but still endoscopically unhealed (LA grades A or B) after 8 weeks history of standard treatment healing course with PPI, designed to support dose selection for Phase 3. The pronounced acid control of X842 is assumed to provide high endoscopic healing rates already after 4 weeks treatment course. The four dose levels of X842 are selected based on data from the Phase 1 studies where the 50 mg twice daily (BID) dose displayed an acid control slightly stronger than observed for standard PPI. The dose selection for Phase 3 will be based on the proportion of endoscopic healing following each dose of X842, the respective safety data and the pharmacokinetic (PK) profile. Lansoprazole will serve as an active comparator.

Objectives and Endpoints

Objectives	Endpoints
Primary	
The primary objective of the study is to support dose selection for X842, through assessment of healing of erosive esophagitis due to GERD after 4 weeks of treatment.	Healing of erosive esophagitis due to GERD based on endoscopic assessment after 4 weeks of double-blind treatment.
Secondary	
Evaluate the safety and tolerability of the four dose levels of X842 and lansoprazole, where lansoprazole will serve as the active comparator.	Physical examination, weight, body mass index (BMI), vital signs, electrocardiogram (ECG) recordings, safety laboratory measurements (hematology/clinical chemistry/urinalysis), adverse event (AE), treatment emergent adverse event (TEAE), adverse event of special interest (AESI), serious adverse event (SAE) reporting, concomitant medication(s).
Evaluate the reflux related symptom pattern during the initial 4 weeks treatment with four dose levels of X842 and with lansoprazole, and the symptom pattern during the subsequent additional 4 weeks (Weeks 5-8) open-label treatment with lansoprazole 30 mg QD	
Percentage of heartburn-free 24-hour days during the Weeks 1-8 (Visits 2-9) based on eDiary (RESQ-eDiary), including splits into day- and nighttime evaluations.Percentage of 24-hour days with at most mild heartburn symptoms during the Weeks 1-8 (Visits 2-9) based on eDiary (RESQ-eDiary), including splits into day- and nighttime evaluations.Investigator assessment of symptom at Weeks 1-8 (Visits 2-9)Reflux related symptoms as measured by change from baseline in QOLRAD score assessed after 1, 2, 4 and 8 weeks of treatment
Exploratory	
CCI	CCI
CCI	CCI

Overall Design:

The study will be conducted in multiple centers in Europe and the US. This will be a randomized, double-blind, active comparator-controlled study with a parallel group design including four arms with X842 and one arm with lansoprazole. Pharmacokinetic (PK) blood sampling pre-dose, before the first and the second dose administration will be performed at Day 7, Day 14 and Day 28 visits in all patients. Approximately 240 patients with erosive esophagitis due to GERD LA grade C or D and patients with erosive esophagitis due to GERD LA grade A or B with at least partial symptom response but still endoscopically unhealed after 8 weeks history of standard treatment healing course with PPI, will be randomized in order to have 200 evaluable patients.

Randomization to one of the treatments with X842 twice daily (BID) 25 mg, 50 mg, 75 mg, 100 mg, or lansoprazole 30 mg once daily (QD) will be based on a 1:1:1:1:1 scheme. One site cannot enroll more than 20% of the overall number of patients (48 patients).

The duration of each patient's participation in the study, including screening, blind treatment period and open-label treatment period will be approximately 60 days. The patients will be randomized for 4 weeks (28 days, -2/+5 days) double-blind treatment and will be provided with investigational medicinal product (IMP) for 35 days (including one additional blister pack dispensed at Visit 2/Day 0) to allow for treatment up to the visit window. All patients will have an endoscopic evaluation after 4 weeks treatment. Following the endoscopic evaluation, all patients will receive subsequent 4 weeks open-label treatment with lansoprazole 30 mg QD. Repeated symptom evaluation to detect symptom pattern will be assessed during this period.

Randomization ratio	TREATMENT GROUP	Morning capsule	Morning tablet 1	Morning tablet 2	Evening tablet 1	Evening tablet 2
1	X842 (BID) 25 mg	placebo	25 mg	placebo	25 mg	placebo
1	X842 (BID) 50 mg	placebo	50 mg	placebo	50 mg	placebo
1	X842 (BID) 75 mg	placebo	50 mg	25 mg	50 mg	25 mg
1	X842 (BID) 100 mg	placebo	50 mg	50 mg	50 mg	50 mg
1	Lansoprazole (QD) 30 mg	30 mg	placebo	placebo	placebo	placebo

Number of Patients:

[figure not shown]
The number of patients in the study will be approximately 240; 48 patients in each treatment arm.

Treatment Groups and Duration:

Four doses of X842 (25 mg, 50 mg, 75 mg, 100 mg, and dummies) will be administered as tablets twice daily. The active comparator lansoprazole 30 mg and its dummy will be administered as capsules once daily in the morning. The study drugs should be taken with 100 mL of noncarbonated water at least 30 minutes prior to meals. The duration of double-blind treatment will be 28 days -2/+5 days. To blind treatment, each patient will receive 2 tablets (containing doses of X842 or its dummy) and one capsule (containing lansoprazole or its dummy) in the morning and 2 tablets (containing doses of X842 or its dummy) in the evening.

